	Action Measures: values identification and discussions	25	Action Measures: ICC*= 0.87 (0.79-0.92) ²⁷							
Implementation: Acceptability	Acceptability and Usability (a) Ease of Use and Understanding (b) Usefulness in decisions & discussions (c) Attitudes about norms or expectations	8 6 6	1 factor explained 81-85% of variance/scale. Kuder- Richardson >0.75 ⁸	1 factor explained 81- 85% of variance/scale. Kuder-Richardson >0.75 ⁸	x					
	Adverse Event Outcomes									
Depression	Patient Health Questionnaire- 8	8	Scores ≥10 100% sensitive and 95% specific for major depressive disorder. ^{73,74}	Scores ≥10 77% sensitive and 100% specific for major	x	x	x	x	x	
Construct	Measure	# items	English Reliability/Validity	Spanish Reliability/Validity	Baseline	1 week	3 months	6 months	12 months	15 months
------------------------------------	--	---------	--	---	----------	--------	----------	----------	-----------	-----------
				depressive disorder ⁸²						
Anxiety	GAD-7 ⁷⁵	7	Cronbach's α = 0.92 ⁷⁵ ICC*= 0.83	Cronbach's $\alpha = 0.88^{76}$ ICC*= 0.64	х	х	х	х	х	
	Exploratory Outcome									
Percent increase in ACP activities	N (%) participants who increased their Behavior Change or Action scores from baseline (i.e., estimated slope > 0)		-	-	x	x	x	x	x	
	Demographic Information									
Demographic Information	Age, gender, race/ethnicity ⁸³ , marital status, and education				x					
Finances	"In general, how do your finances usually work out at the end of the month?"	1	Associated with functional impairment and co-morbidity ⁸⁴	-	x					
Socioeconomic Social Standing	Social standing ladder (i.e. place an "x" where you think you stand relative to other people in society)	1	Associated with functional decline ⁸⁵	-	x					
	Other Measures									
Health Literacy	Short form Test of Functional Health Literacy in Adults s- TOFHLA, scores 0-36) ⁷⁷ Continuous & dichotomized to limited = 0-22 & adequate	36	Cronbach's α = .97 Correlation coefficient w/ other literacy tests > 0.80 ⁷⁷	Cronbach's α >.95 ⁸⁶	x					

Construct	Measure	# items	English Reliability/Validity	Spanish Reliability/Validity	Baseline	1 week	3 months	6 months	12 months	15 months
	= 23-36									
Patient-clinician language concordance	To clinicians: "How well do you speak Spanish? ⁸⁷ Fluent, very well (concordant) vs. well, fair, or poor"	1	AUROC [†] 94% (CI: 90- 98%) ⁸⁷	AUROC [†] 94% (CI: 90- 98%) ⁸⁷	х					

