1649 Our primary analyses will compare change in ACP documentation between study arms from 1650 baseline to 15 months. Secondary outcomes will include ACP Engagement with respect to 5 1651 ACP Actions (yes/no and a 0-25-point scale) and behavior change scores (average 5-point 1652 Likert scores) from baseline to 1 week, and 3, 6, and 12 months. Variables will be assessed for distributional and outlier values using standard summary statistics. Baseline comparability will 1653 1654 be assessed between groups using unpaired t-tests, Chi-square tests or Fisher's exact tests. 1655 Using t-tests or Chi-squared tests, we will also compare patient's age and self-reported gender 1656 between those who refused versus those who enrolled and differences between arms of those 1657 who withdrew versus those who did not. We will use intention-to-treat analysis using SAS 1658 version 9.4 (SAS Institute Inc.) and STATA 15.0 (College Station, TX). All p-values will be 2-1659 tailed and set at .05 for the primary outcome and Bonferroni adjusted for secondary patient-1660 reported outcomes. In addition, because of differences in ACP engagement among English and Spanish speakers,⁸ and based on preferences of our stakeholders and granting agencies, we 1661 1662 decided, a priori, to analyze our results overall and stratified by English and Spanish language. 1663 To compare outcomes between the two arms longitudinally, we will use mixed effects linear, 1664 Poisson, or negative binomial regression for continuous measures and mixed effects logistic regression for dichotomous measures. The mixed effects models will include fixed effects for the 1665 1666 primary modeling terms of time (baseline and 15 months for ACP documentation and baseline 1667 and 1 week, 3 months, 6 months, and 12 months for ACP Engagement with time modeled using 1668 dummy variables to allow for non-linearity); arm (AD-only versus PREPARE); an interaction 1669 term of study arm and time; and a random effect for subjects. We will adjust for the randomization blocking factors limited vs. adequate literacy,⁹⁸ and any predictor variables that 1670 1671 differ between arms. All models also will also be adjusted for baseline ACP documentation and will include random physician intercepts to account for nesting of patients within physicians. We 1672 1673 will use standardized, clinically meaningful effect sizes (i.e., 0.20-0.49 small, 0.50-0.79 medium,

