and ≥ 0.80 large).⁹⁹ Per stakeholder request, we will conduct post-hoc mixed-effects regression to calculate the percentage of participants who increased their Behavior Change score, Action scores, or both Behavior Change and Action scores from baseline (i.e., estimated slope > 0) by study arm; p-values adjusted to a significance of 0.017.

1678

1679 For moderator analysis, we will test for interactions by adding interaction terms to the group by 1680 time variable for health literacy (limited versus adequate) controlling for prior ACP 1681 documentation and clustering effects by clinician. All other interaction terms are adjusted for 1682 health literacy (randomization blocking variable) prior ACP documentation and clustering effects 1683 by clinician. Additional interaction terms to be added to the group by time variable include 1684 language (i.e., English versus Spanish), control preferences for decision making (i.e., makes 1685 own decisions versus doctor makes decisions), age (i.e., < 65 years versus \geq 65 years of age), 1686 sex/gender (i.e., self-reported man versus woman), race/ethnicity (i.e., white versus non-white), 1687 health status (i.e., good-to-excellent versus fair-to-poor), presence of a potential surrogate (i.e., 1688 yes versus no), internet access at home (i.e., yes versus no), and, for Spanish-speakers, 1689 patient-clinician language (concordance vs. discordance). A p-value for interaction <0.05 is 1690 considered significant. 1691

Missing data for the primary outcome will be assessed. If there is 10% or more of missing data, we will use a mean imputation approach. All available data will be included in mixed-effects models. We will assess whether any research staff member became unblinded during follow-up assessment and conduct sensitivity analysis as needed.

1696

1697 SAMPLE SIZE AND POWER CALCULATIONS

1698 We will measure a full range of ACP behaviors including discussions. However, written advance 1699 directive completion of legal forms is a primary outcome and is the most well-studied.¹⁰⁰ Power

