1700 from longitudinal analyses with repeated measures will be stronger, but to be conservative, we consider power for a single post-intervention time point (e.g., 15 months). A recent meta-1701 1702 analysis of written advance directive documentation studies demonstrated a pooled effect size of 0.50 (95% CI; 0.17 -0.83),¹⁰⁰ as did an RCT of an ACP workbook that included both behavior 1703 change constructs and a social work visit,¹⁰¹ and our prior RCT of an easy-to-read AD at ZSFG 1704 which showed an increased AD completion rate from 7% to 15%.⁸ Because both the 1705 1706 intervention and control arm will receive the easy-to-read advance directive, we assume that 1707 both arms will have an advance directive completion rate of $\leq 15\%$. Based on prior studies, we 1708 assume PREPARE will result in additional benefit of advance directive completion with a 1709 minimum effect size of 0.5 (two-fold increase) above 15%. A sample of 350, (175 per arm), will 1710 afford us 92% power (2-tailed alpha of 0.05) to detect a difference of advance directive 1711 completion rates of 15% in controls vs. 30% in the PREPARE arm and 80% power to detect a difference of 15% vs. 27%. Power is also expected to be strong for the ACP behavioral change 1712 scale outcomes (preliminary data demonstrated a pre-to-post improvement of 0.5 SD).²⁷ With a 1713 1714 conservative assumption that controls will improve by 0.1 to 0.2 SD, we will have 85% to 98% 1715 power, respectively, to conclude that the improvement is better in the PREPARE arm. We 1716 expect a 15% drop out rate at 12 months based on our prior randomized, controlled trial at ZSFG,⁸ and will therefore attempt to recruit 402 patients, or 201 in each arm for each language 1717 1718 (English and Spanish) for a total recruitment of 804 patients.

1719

Our sample size will also allow adequate power to detect clinically important interactions based on potential moderators (literacy, control preferences, language concordance) for our outcomes. In a prior trial of an easy-to-read advance directive in the same patient population with only 200 patients, we found significant interactions for literacy.⁸ Thus, if we consider the power scenario of the control group ACP documentation rate of 15% and the PREPARE group of 28%, and suppose the control group rate is the same (15%) for both levels of the moderating factor, then

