1726 for a moderating factor split of 1:1, we would have 80% power to detect an interaction. If the 1727 PREPARE arm ACP documentation rate is 18% for one level of the factor and 40% for the 1728 other, this corresponds to a relative rate of ACP documentation of 2.2 times as high for one 1729 level of the factor compared to the other. A 2:1 split of the moderating factor still allows 1730 detection of a 2.4-fold increase in the relative rate of documentation. Power to detect 1731 interactions will likely be stronger for continuous outcomes (e.g. engagement/behavioral scales). 1732

ETHICS AND ADVISORY COMMITTEES 1733

1734 This study is approved by the University of California, San Francisco (UCSF) (IRB reference 1735 #13-10847). This study is guided by a Patient-Clinical Stakeholder Advisory Board that is 1736 comprised of patients and patient advocates (including native Spanish-speakers), surrogates, 1737 and ZSFG/SFHN primary care clinic staff and medical directors. It is also guided by a DSMB 1738 consisting of 4 experts in randomized trials, human subjects research and consent, vulnerable 1739 populations, palliative care, advance care planning, and biostatistics. Both advisory groups 1740 reviewed and approved all study protocols and related materials. In addition, we continue to 1741 meet with both groups every 4-6 months to review the progress of the trial, make suggestions 1742 for recruitment, review any potentially adverse events, and ensure that we are following our 1743 study protocols in a way that protects vulnerable patient populations.

1744

1745 **HUMAN SUBJECTS PROTECTIONS**

1746 Protection of the rights and welfare of participants:

1747 All study staff are required to take annual training regarding the rights and protections of 1748 research participants. Additionally, weekly study team meetings will ensure that all study staff 1749 are following the research protocol and that all study participants are consented according to 1750 our study protocol.

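### Power section: the behaviour-scale powers are in reverse order, and the 80% interaction power states no N or scale although language concordance is tested only in Spanish-speakers (unadjusted, assumed 1:1 split: about 52–58% on log-odds, 73–79% on risk difference)

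*Combined protocol and SAP*

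**What the plan says.** All references are to the final protocol (September 2017).

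**Behaviour scale.** Sample Size and Power Calculations takes a pilot gain of 0.5 SD for PREPARE and then says: "conservative assumption that controls will improve by 0.1 to 0.2 SD, we will have 85% to 98" per cent power, with the two values paired respectively. That sentence gives no n, test or baseline correlation. The same paragraph sizes the trial on advance-directive rates: "A sample of 350, (175 per arm), will" give 92% power for 15% v 30% and 80% for 15% v 27%. It says that, to be conservative, it will "consider power for a single post-intervention time point (e.g., 15 months"). Allowing for 15% dropout, it plans to recruit 402 patients per language (201 per arm), 804 in all.

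**Interactions.** The next paragraph claims adequate power for interactions based "on potential moderators (literacy, control preferences, language concordance) for our outcomes". The illustration has 15% in controls at both levels and 18% v 40% under PREPARE: "for a moderating factor split of 1:1, we would have 80% power to detect an interaction". It adds that a 2:1 split still allows a 2.4-fold increase in the relative rate to be detected. Neither statement gives N or scale.

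**How concordance is tested.** The moderator analysis in the Statistical Analysis Plan lists "internet access at home (i.e., yes versus no), and, for Spanish-speakers", patient-clinician language concordance, with interactions judged at p<0.05. The model is "mixed effects logistic regression for dichotomous measures". The Outcome Measures Table defines concordance by the clinician's self-rated Spanish: fluent or "very well (concordant) vs. well, fair, or poor". No expected split is given.

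**Outcome label.** The power section calls completion of advance-directive legal forms a primary outcome. Measures, Primary Outcome, defines the primary outcome as new ACP documentation, a composite of forms and/or documented discussions.

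**The concern.** A larger gain in controls leaves a smaller difference to detect, so the higher power cannot belong to the larger control gain. The sentence is wrong as printed, whatever n or test lies behind it.

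The interaction claim names three moderators together. Literacy and control preferences can be tested in both languages combined, but concordance is confined to one language, about half the patients. Concordance is named in the second study aim. If its interaction test is null, the power section is where a reader would look to judge how informative that result is. That section offers adequate power and an 80% illustration, without the N or scale needed to see whether they apply to this test.

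The outcome label is a smaller matter: it puts one component of the composite on the footing of the primary outcome.

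**Working it through.** **1. Reproducing the advance-directive powers.** Inputs: 175 per arm, two-sided alpha 0.05. Power = Φ[(Δ − 1.96·SE0)/SE1], with SE0 pooled and SE1 unpooled.
- 15% v 30%: SE0 = √(2×0.225×0.775/175) = 0.0446; SE1 = √((0.1275+0.21)/175) = 0.0439; power = Φ(1.423) = 92.3% (stated 92%).
- 15% v 27%: SE0 = 0.0435; SE1 = 0.0431; power = Φ(0.805) = 79.0% (stated 80%).

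Both agree with the plan, so 175 per arm is their basis.

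**2. Behaviour scale.** Net differences: 0.5 − 0.1 = 0.4 SD and 0.5 − 0.2 = 0.3 SD. Normal approximation: power = Φ(d·√(n/2) − 1.96).
- n = 175: Φ(3.742 − 1.96) = 96.3%; Φ(2.806 − 1.96) = 80.1%.
- n = 201: Φ(4.010 − 1.96) = 98.0%; Φ(3.008 − 1.96) = 85.3%.

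| Basis (t-test or ANCOVA) | Controls +0.1 SD | Controls +0.2 SD |
|---|---|---|
| As printed | 85% | 98% |
| 175 per arm, unadjusted | 96.2% | 79.9% |
| 201 per arm, unadjusted | 97.9% | 85.1% |
| 175 per arm, ANCOVA, baseline correlation 0.35 | 97.9% | 84.8% |
| 175 per arm, ANCOVA, baseline correlation 0.5 | 99.1% | 89.8% |

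Power falls from left to right on every computed basis. Swapped, the printed pair fits two of them.

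**3. Interaction, 1:1 split.** Four independent cells of n = N/4, with controls at 15% and 15% and PREPARE at 18% and 40%. Wald test, two-sided 0.05, without covariates, clinician clustering or the baseline time point. Power = Φ(δ/√(V/n) − 1.96), where V sums the four unit variances.
- Log-odds: δ = ln(0.40/0.60) − ln(0.18/0.82) = 1.111; V = 7.843 + 7.843 + 6.775 + 4.167 = 26.63.
  - N = 350 (n = 87.5): Φ(2.014 − 1.96) = 52.1%.
  - N = 402 (n = 100.5): Φ(2.158 − 1.96) = 57.9%.
- Risk difference: δ = 0.22; V = 0.1275 + 0.1275 + 0.1476 + 0.24 = 0.6426.
  - N = 350: Φ(2.567 − 1.96) = 72.8%.
  - N = 402: Φ(2.751 − 1.96) = 78.6%.
- N for 80% power = 4 × 7.849 × V/δ²: 678 on log-odds, 417 on risk difference.

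| N | Log-odds | Risk difference | Log relative rate |
|---|---|---|---|
| 350 | 52.1% | 72.8% | 43.3% |
| 402 | 57.9% | 78.6% | 48.4% |
| 700 (2 × 350, both languages) | 81.3% | 95.3% | 71.7% |
| N needed for 80% | 678 | 417 | 857 |

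Simulation (60,000 runs) gives 52.4% and 57.7% on log-odds, and 73.2% and 78.5% on risk difference, at 350 and 402.

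**4. The plan's 2:1, 2.4-fold statement.** Assume an overall PREPARE rate of 28%, the figure in the same paragraph. If the larger level has the lower rate, the rates are 0.84/4.4 = 19.1% and 45.8%. If it has the higher rate, they are 0.84/5.8 = 14.5% and 34.8%.

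| N | Log-odds (lower / higher rate in larger level) | Risk difference (same order) |
|---|---|---|
| 350 | 60.8% / 46.2% | 81.1% / 65.8% |
| 402 | 66.8% / 51.5% | 86.1% / 71.8% |

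If the 18% v 40% contrast is kept at 2:1 instead, power is 46–49% on log-odds and 66–70% on risk difference at 350, and 52–54% and 72–76% at 402.

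**The case against.** The strongest reply concerns the interaction. The plan does not say how the 80% was obtained. Risk difference with all 402 patients in one language gives 78.6%, about as close to 80% as the 79.0% that reproduces the stated 80% for 15% v 27%. The figure may therefore have been derived properly for a single language. Using 402 is also defensible: the 15% dropout refers to 12 months, the last interview, whereas documentation comes from chart review at 15 months, so a missed interview need not remove a patient. This stands. A reader might infer that the 80% is a miscalculation, or was computed on the pooled sample and wrongly carried over to concordance. The documents support neither, because N and scale are not given. What remains is that risk difference is not the scale of the planned logistic interaction, and that power on it is 73% at 350.

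The four-cell test is also not the planned mixed model with baseline adjustment and clinician intercepts, and the split is assumed. That is why the result is given as a range. At the plan's own 2:1, 2.4-fold effect, risk-difference power lies on either side of 80%, so it would be wrong to say that a 2:1 split always lowers power.

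On the behaviour scale, the error is a transposition in a secondary-outcome sentence. Sample size was set on advance-directive rates, and every reordered basis shown in the check gives about 80% or more. A reader might infer that dropout was ignored, because 98% and 85% match 201 per arm. A baseline correlation of about 0.35 at 175 per arm does equally well, so the documents do not settle it.

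On the label, the section names advance-directive completion wherever it gives 92% and 80%, so misreading them as power for the composite is unlikely.

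**Conclusion.** The behaviour-scale sentence is wrong as written. This is certain and needs no assumption about n. The correct values are 96% and 80% at 175 per arm unadjusted, or 98% and 85% on a basis the plan would have to state.

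The interaction claim is incomplete rather than shown to be wrong. For concordance in 350–402 Spanish-speakers, power for the illustrated contrast is about 52–58% on log-odds and 73–79% on risk difference. This assumes a 1:1 split and independent cells without covariates or clustering. On log-odds, 80% needs about 678 patients, close to both languages pooled. Confidence in the concordance figures is moderate, because N, scale and split all had to be supplied.

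The outcome label is a minor wording point.

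A reader might infer that the trial is underpowered for its main comparison. Nothing here shows that: the 92% and 80% for advance-directive completion reproduce.

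**What to change.** Wording only, in Sample Size and Power Calculations:

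1. Print the behaviour-scale powers as 96% to 80%, respectively, adding 175 per arm, two-sided alpha 0.05 and no baseline adjustment. Alternatively print 98% to 85%, respectively, together with the basis that produces it: 201 per arm with no dropout, or the baseline correlation assumed.
2. State the N and scale behind the 80% and behind the 2:1, 2.4-fold statement. Then either limit the claim to moderators tested in the pooled sample, or add the Spanish-only power for concordance with its scale and split. For example: about 52–58% on log-odds (73–79% on risk difference) in 350–402 patients, unadjusted, assuming a 1:1 split.
3. Minor: describe advance-directive completion as a component of the primary composite outcome.

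The cost is a less favourable stated power for concordance. No patients are added and no analysis changes.

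### The recruitment target of 402 per language appears to come from 350 × 1.15 rather than 350 / 0.85, so it keeps 350 evaluable patients only if loss is at most 12.9%, not the expected 15%

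*Combined protocol and SAP*

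**What the plan says.** The final protocol, under Sample Size and Power Calculations, states the number on which its power rests: "A sample of 350, (175 per arm), will" "afford us 92% power (2-tailed alpha of 0.05) to detect a difference of advance directive" "completion rates of 15% in controls vs. 30% in the PREPARE arm and 80% power to detect a" "difference of 15% vs. 27"%. It then says that the investigators "expect a 15% drop out rate at 12 months based on our prior randomized, controlled trial at" the same hospital, and that they "will therefore attempt to recruit 402 patients, or 201 in each arm for each language" ("English and Spanish) for a total recruitment of 804 patients"). The earlier protocol in the same file carries identical figures.

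Three other places bear on the point:

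- The Statistical Analysis Plan section commits "to analyze our results overall and stratified by English and Spanish language", so the number in each language has a use of its own.
- Under Primary Outcome and in the Outcome Measures Table, the primary outcome is new documentation in the medical record, found by chart review at baseline and 15 months. The patient-reported outcomes come from interviews up to 12 months.
- The Statistical Analysis Plan section provides for imputation if 10% or more of the primary outcome is missing.

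**The concern.** The target of 402 is presented as what follows from needing 350 and expecting to lose 15%. The two figures do not fit: removing 15% from 402 does not leave 350. Multiplying the required number by one plus the dropout rate is a common slip. The loss falls on the inflated number, so the required number has to be divided by one minus the rate.

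At stake is whether the stated power belongs to the stated recruitment. The 350 is a per-language figure, since the allowance turns it into 402 for each language. The pooled analysis therefore does not settle the matter for the language-specific comparisons.

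**Working it through.** **Inputs, all from Sample Size and Power Calculations:** 350 evaluable per language (175 per arm, 1:1); two-sided alpha 0.05; control 15%; PREPARE 30% or 27%; dropout 15%; target 402 per language (201 per arm), 804 in total.

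**1. Reproduce the stated power at 175 per arm.** Two proportions, normal approximation, pooled variance under the null:

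power = Φ{ [ |p1 − p2| − 1.96 √(2 p̄(1 − p̄)/n) ] / √( [p1(1 − p1) + p2(1 − p2)]/n ) }

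For 15% vs 27%, p̄ = 0.21 and the two square roots are 0.04354 and 0.04307. Power = Φ[(0.12 − 1.96 × 0.04354)/0.04307] = Φ(0.805) = 79.0%. For 15% vs 30% the formula gives 92.3%. With unpooled variance the results are 79.6% and 92.7%. The plan's 92% is reproduced. Its 80% is reproduced only after rounding up from 79.0–79.6%.

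**2. Reproduce the target.**

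- 350 × 1.15 = 402.5 and 175 × 1.15 = 201.25. Rounded down, these are the plan's 402 and 201.
- 350 / 0.85 = 411.8, so 412 per language (206 per arm), or 824 in total.

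**3. What 402 delivers.**

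- 402 × 0.85 = 341.7 per language, or 170.85 per arm. This is about 8 short of 350.
- 1 − 350/402 = 12.9%, the largest loss at which 350 remain.
- Both languages together: 804 × 0.85 = 683, against 700.

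**4. Power by number evaluable per arm.** For 15% vs 27% at 170.85 per arm, pooled: Φ[(0.12 − 1.96 × 0.04407)/0.04359] = Φ(0.772) = 78.0%.

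| Evaluable per arm | 15% vs 30%, pooled | 15% vs 30%, unpooled | 15% vs 27%, pooled | 15% vs 27%, unpooled |
|---|---|---|---|---|
| 175 (plan's basis) | 92.3% | 92.7% | 79.0% | 79.6% |
| 170.85 (402 less 15%) | 91.7% | 92.1% | 78.0% | 78.6% |
| 201 (no loss) | 95.2% | 95.5% | 84.2% | 84.8% |

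**5. Split the gap for 15% vs 27%.** From the stated 80% to the pooled 78.0% is 2 points. The step from 175 to 170.85 per arm accounts for 79.0 − 78.0 = 1.0 point (unpooled 79.6 − 78.6 = 1.0). The remainder is present at 175 per arm, before any dropout.

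**6. Interview-based scale outcomes.** The plan assumes a 0.5 SD improvement with PREPARE and 0.1 to 0.2 SD in controls, so differences of 0.4 to 0.3 SD. A plain two-sample comparison with SD 1 (my assumption; the plan does not print its method here) gives 80.1% for 0.3 SD and 96.3% for 0.4 SD at 175 per arm. At 170.85 per arm the figures are 79.2% and 95.9%. These are not the plan's 85% and 98%. They show only that the shift is again 1 point or less.

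**The case against.** The strongest objection is that the 15% is an interview dropout rate, while the 92% and 80% concern documentation read from charts. A patient who stops answering calls still has a medical record, and the plan specifies intention-to-treat with all available data in the models. If charts are complete for everyone randomised, 201 per arm are evaluable and power is 95.2% and 84.2%, both above what is claimed. This stands as far as it goes: for the primary outcome the evaluable number lies somewhere between 342 and 402 per language, and the documents do not say where. They do not promise complete chart data, they do not say whether a patient who withdraws remains open to chart review, and they provide for 10% or more missing primary data. Nor does the sample size section separate chart from interview outcomes when it applies the allowance. The scale outcomes for which that section also claims power do depend on interviews, so the loss reaches them directly.

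It can also be said that 350 × 1.15 is a guess, since no formula is printed. That is true, but the mismatch between 402, 15% and 350 holds however 402 was reached.

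Finally, the gap is 10 patients in 412 (2.4%), and the pooled analysis has ample power even after the loss: with about 342 per arm, 99.7% and 97.2% by the same formula. Both are correct. They limit the point to a restatement, but they do not make the per-language figures agree.

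**Conclusion.** The point holds as an internal inconsistency of small size. With the dropout rate that the plan expects, 402 per language gives about 342, not 350. If dropouts lose their outcome data, the stated 92% survives (91.7–92.1%), and power for 15% vs 27% is about 78% (78.0–78.6%) against the stated 80%. About 1 point of that difference comes from the inflation.

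Three stronger readings might be inferred, and the documents do not support them:

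- *That the trial falls short of its evaluable number on the primary outcome.* This would require that dropouts lose their chart data, which the plan does not say.
- *That the dropout error costs 2 points of power.* About half of that gap exists at 175 per arm and is a matter of formula and rounding.
- *That more patients must be enrolled.* Neither power changes enough to alter the design.

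The figures assume the plan's own rates, 1:1 allocation, equal loss in both arms and a single time point. They make no allowance for clustering by physician.

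**What to change.** Keep 402 per language and replace the dropout sentence in Sample Size and Power Calculations with one of two statements.

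1. With 15% dropout, about 342 per language (171 per arm) are evaluable, giving about 92% power for 15% vs 30% and about 78% for 15% vs 27%. This applies if chart data are lost with dropout. The scale outcomes should be restated at the same number.
2. The primary outcome is obtained by chart review for everyone randomised, so no allowance is made for it; at 201 per arm, power is about 95% and 84%. The 15% allowance, and about 342 per language, then apply to the survey outcomes only.

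The team must decide which is true, in particular whether chart review continues after a patient withdraws from interviews. The cost is a sentence or two and a rerun of the scale-outcome power. Enrolment, design and analysis do not change. If the team prefers to keep 350 evaluable under 15% loss, the matching target is 412 per language (824 in total), but the gain does not require it.
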